The change from the traditional Mexican diet to a Western diet, generated by the nutritional transition, has not only generated prevalence's of more than 75% of metabolic alterations (obesity, type 2 diabetes, cardiovascular diseases, dyslipidemia) (1–3) and in the gut microbiota of the Mexican population (4), but it has also generated the water and carbon footprint of their diet to be the highest in the world with more than 8,000 Liters per person per day ($L\ p^{-1}d^{-1}$) (5) and 6.01 Kg $CO^2eq\ p^{-1}d^{-1}$ (6), respectively. This is linked to the aggravation of climate change, with increases of more than 1.0 °C in the average atmospheric temperatures (7) and the current water crisis that Mexico is going through, which affects 85% of the territory and has been referred to as the worst water drought in history, affecting the water supply of millions of Mexicans (1,8).

One of the proposals for the joint solution of these problems has been the adoption of sustainable and territorial diets, which in Mexico could be carried out through the recovery of its traditional diet, both pre-Hispanic and colonized, which, prepared with low-fat culinary techniques and low content of animal products, can be considered as an appropriate option from a nutritional, cultural, economic and environmental perspective, dimensions that must be present for a diet to be considered as sustainable (1,9–12).

However, to achieve the adoption of a particular diet, it is necessary to modify the eating behavior of the population (13–15). To modify both dietary and unsustainable behaviors in a population, there are multiple strategies, among which intervention programs have stood out (14,16,17). However, to date and both nationally and internationally, no intervention program whose objective is to promote both adequate nutrition to improve health and reduce the environmental impact of dietary behaviors, has been reported. This respecting cultural, social, economic, and psychological aspects of the population.

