Based on the above, this study protocol aims to design a three-stage 15 weeks intervention program, based on the guide to designing interventions of the behavior change wheel model (14), which includes both nutritional and sustainability elements, in the sense of considering unsustainable dietary behaviors of the Mexican population, in addition to taking into account their social, cultural and economic aspects. In addition to these axes, the basis of behavioral modification intervention programs is psychology. Therefore, it is proposed to design a sustainable-psycho-nutritional intervention program, whose objective is to promote the adherence of the population to sustainable diets. But, in addition, it is proposed to evaluate its effects on environmental indicators, metabolic biomarkers, and gut microbiota, as well as clinical aspects and body composition in a Mexican population sample. Because of the effectiveness of technologies use in nutritional (18,19) and environmental (20,21) interventions,

the intervention program will be a digital one, for which a mobile application is being designed to evaluate and monitor the intervened population. Therefore, this will be a m-Health intervention program.

We hypothesized that a sustainable-psycho-nutritional intervention digital program can modify the eating behavior of a Mexican population group and guide it towards a sustainable diet, generating decreases in glucose levels, total cholesterol (TC), LDL cholesterol (LDL-C), and triglycerides (TG), and increases in HDL cholesterol (HDL-C) levels. Likewise, we hypothesized that this type of program can modify the composition of the gut microbiota of the population, promoting the proliferation of bacteria related to metabolic health; reduce the water and carbon footprint of the sample's diets; maintain adequate body fat levels in the population with an adequate body fat percentage or reduce them in the overweight or obese population; maintain blood pressure levels in the healthy population and lower them in the population with high blood pressure, and reduce the presence of acanthosis nigricans.

2. Methods

It is proposed to carry out a quasi-experimental longitudinal study of three stages that will be related to each other.

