D) Dietetics: caloric-nutritional intake will be assessed through 24-hour recalls and dietary records (51), and by a validated adapted Food Frequency Questionnaire (CFCA) (5,52). Diet quality will also be analyzed by an adapted version of the Mexican Diet Quality Index (ICDMx) (53). Participants will also be asked about food preparation, food shopping places, food allergies and intolerances, food preferences, and about following specific diets at the moment of the evaluation.

E) Environmental: dietary water footprint will be calculated using the Water Footprint Assessment method (54) in its version for Mexico's context (5). The water footprint of each food and food ingredients are going to be calculated. Also, water involved in cooking and food washing is going to be evaluated. Dietary carbon footprint is also going to be calculated using the Life Cycle Assessment method (7,55,56). Food system boundaries are going to be the impact of food production and processing on greenhouse gas emissions, as carried out by Fresán et al. (57). Corrections factors from converting cooked to uncooked food and peeled to unpeeled food are going to be applied. Both calculations are going to be performed in the Nutriecology® Software.

S) Socioeconomic level and cultural aspects: educational level, occupational level, and economic income are going to be evaluated according to classifications used for Mexico, which are detailed in Supplementary Material 3 (58). For this aspect, food prices are going to be investigated in fieldwork and in supermarket databases, in order to promote the consumption of accessible foods. Also, food culture related to celebrations and traditions is going to be investigated.

N) Nutritional-sustainable knowledge: it will be evaluated through a designed questionnaire (Supplementary Material 4), based on the psychological capacity presented in the COM-B model. It will include a series of questions for the evaluation of nutritional-sustainable knowledge, which will be related to the established behavioral objectives and will be based on manuals for the design of nutritional knowledge questionnaires and on questions on sustainable food consumption (59–62).

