2.3.4 Statistical analyses

The distribution of the data will be analyzed with the Kolmogorov Smirnov test. Descriptive analysis will be performed, including means, standard deviations, and medians. Next, the effects of the program on the selected variables will be assessed by comparing them between evaluations and between groups with t-student tests for paired and unpaired data, respectively, if a normal distribution is found. For no normally distributed data, the Wilcoxon test (repetitive measures) and the U de Mann Whitney test (independent groups) will be used. For no categorical variables, the chi-squared test will be used. Correlation analyses will also be performed, considering Pearson correlation for normally distributed data and Spearman correlations for no normally distributed data. Likewise, simple, and multiple linear regression models will be carried out, as well as binary logistic regression analysis, to identify relationships and risks between variables. Statistical analysis will be performed at STATA V12® program.

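### The footprint outcome has no stated unit and no energy or baseline adjustment, so a between-arm fall cannot be split into diet composition, amount eaten and under-reporting

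*Combined protocol and SAP*

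**What the plan says.** Section 2.2.3, part E, states that "dietary water footprint will be calculated using the Water Footprint Assessment method" and that "Dietary carbon footprint is also going to be calculated using the Life Cycle Assessment method". The water footprint is built food by food, with washing and cooking water considered. Conversion factors for cooked and peeled food are applied. No outcome unit is given. The only scale in the text is in the Introduction, for national figures: "more than 8,000 Liters per person per day" for water, and 6.01 kg CO2eq per person per day for carbon.

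Part D of the same section says that "caloric-nutritional intake will be assessed through 24-hour recalls and dietary records", and adds a food frequency questionnaire and an adapted diet quality index. All of these are self-reported. The plan does not say which instrument feeds the footprints.

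In section 2.3.4 "the effects of the program on the selected variables will be assessed" by paired comparisons between evaluations and unpaired comparisons between groups, using t tests or their rank equivalents. Linear and logistic regressions are also planned, to explore relationships and risks, but no outcome or covariate is named. The plan contains no footprint per unit of energy, no energy covariate and no check on the plausibility of reported energy.

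The hypothesis in the Introduction is that the programme can "reduce the water and carbon footprint" of participants' diets. For body fat it also expects to "reduce them in the overweight or obese population".

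**The concern.** A footprint summed over reported foods rises and falls with the quantity reported. Three things can lower it: a different mix of foods, a smaller amount of the same mix, or less complete reporting. The programme's objective is adherence to a sustainable diet, which is largely about the first. The comparison as planned cannot tell the three apart.

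Differential reporting is a concrete risk here. Seven of the 13 behavioural targets in Table 1 are reductions (items 7 to 13). The experimental arm receives two workshops a week for 7 weeks, and a token economy runs on food registers in the app. For fish, chicken, meats, ultra-processed foods and foods high in sugars or fats, Table SM1.4 gives 3 points for a minimum portion and −1 for exceeding the maximum. Participants who attend workshops and collect points know their arm, and no blinding is described. Under-reporting of discouraged foods would move the footprint in the hypothesised direction. The footprints are headline outcomes, so an ambiguous positive result would weaken the trial's main message.

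**Working it through.** **Plan's own figure.** There is none to reproduce. Section 2.2.1 gives 50 per group by reference to a suggested minimum, without an effect size, SD, alpha or power.

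**Inputs from the documents.** 8,000 L/day and 6.01 kg CO2eq/day (Introduction, used only for scale); 50 per arm; and 25 per arm, because section 2.2.1 allows for loss of more than 50% and Table SM2.1 eliminates non-completers.

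**Assumptions (not in the documents).** Differential under-reporting r = 5%, 10% or 20%; between-person CV = 30–50%; two-sided alpha 0.05.

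**Step 1: uniform under-reporting, size of the artefact.** If every food is scaled by (1 − r), the total F becomes F(1 − r), a spurious fall of F × r.

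| r | Water (8,000 × r) | Carbon (6.01 × r) |
|---|---|---|
| 5% | 400 L/day | 0.30 kg/day |
| 10% | 800 L/day | 0.60 kg/day |
| 20% | 1,600 L/day | 1.20 kg/day |

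**Step 2: standardised size.** d = r/CV. For r = 10%, 0.10/0.50 = 0.20 and 0.10/0.30 = 0.33.

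**Step 3: chance of p<0.05 with no true effect.** Two-sample t test with noncentrality d × √(n/2).

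| d | n = 50 per arm | n = 25 per arm |
|---|---|---|
| 0.20 | 0.20 × 5 = 1.00, giving 17% | 0.20 × 3.54 = 0.71, giving 11% |
| 0.33 | 0.33 × 5 = 1.65, giving 37% | 0.33 × 3.54 = 1.17, giving 21% |

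The nominal rate is 5%.

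**Step 4: effect of energy standardisation.** With energy E from the same reports, density is F(1 − r)/[E(1 − r)] = F/E. At an assumed 2,000 kcal this is 8,000/2 = 4,000 L and 6.01/2 = 3.005 kg per 1,000 kcal, before and after, for any r. Uniform under-reporting cancels.

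**Step 5: limit of standardisation.** Suppose discouraged foods carry 40% of the footprint and 15% of energy (assumed), and 20% of them go unreported. The footprint factor is 1 − 0.40 × 0.20 = 0.92, and the energy factor is 1 − 0.15 × 0.20 = 0.97. Density becomes 0.92/0.97 = 0.948 of its true value. The total falls 8.0% and density still falls 5.2%, with no change in diet.

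**The case against.** The strongest reply is that the total footprint is exactly what the hypothesis names. Eating less does lower it, and the protocol expects body fat to fall in some participants. This stands. A reader might infer that any fall due to smaller intake is an artefact, but the documents do not support that: a real reduction is a real saving.

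A reader might also infer that the plan analyses footprints only as absolute daily amounts. That goes beyond the text. The outcome unit is undefined, the per-person-per-day scale appears only for national figures, and regressions with unnamed covariates are planned. What can be said is that no unit and no energy adjustment are specified.

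Composition is also approached elsewhere, through the diet quality index, the food frequency questionnaire and the adherence questionnaire. This is a partial answer: these measures are self-reported too, and none is linked to the interpretation of the footprints.

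The direction of the net bias is not certain either. Targets 2 to 6 ask participants to eat more of some foods, and over-reporting those would raise the total. Finally, coaching on particular foods predicts selective misreporting, which density does not remove (step 5 of the working). So density cannot serve as a test that certifies a real shift.

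**Conclusion.** The concern holds in a limited form. As written, a between-arm fall in footprint cannot be attributed to composition, quantity or reporting, because the plan states no unit, no baseline or energy adjustment and no check on reporting.

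The size is conditional. A 10% uniform reporting gap at a CV of 30–50% inflates the chance of a significant result from 5% to about 17–37% at 50 per arm, or 11–21% at 25 per arm. Neither the CV nor the reporting gap comes from the documents, so these figures show what is possible and do not estimate what will happen. They also model uniform scaling, while the actual pattern may be selective.

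The documents do not support the stronger claim that a footprint result would be spurious. The trial remains usable; the gap is one of interpretation and should be closed before analysis.

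**What to change.** 1. Define the primary scale as footprint per person per day, which matches the hypothesis.
2. Pre-specify beside it a between-arm comparison of footprint per 1,000 kcal (L and kg CO2eq).
3. Adjust both for the participant's baseline value.
4. Name the dietary instrument, and take footprint and energy from the same one. The food frequency questionnaire in Supplementary Material 3 asks about average consumption over the last year, a window longer than the 15-week study.
5. Fix the interpretation in advance. A fall in the total without a fall in density indicates a change in quantity or reporting, not a shift in composition. A fall in density is supportive but not proof, because selective under-reporting of discouraged foods also lowers it.
6. Compare by arm the ratio of reported energy to the metabolic rate recorded in Table SM3.1. Read it with measured weight change, since a low ratio can also reflect real restriction.

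The cost is a short addition to section 2.3.4. Caloric intake, weight and metabolic rate are already among the recorded items, so no new measurement is needed provided they are kept at each evaluation. The drawback is that density removes real savings from eating less, so both versions must always be reported.

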2.3 Stage 3: Effects of the sustainable-psycho-nutritional intervention program

As the last stage of this protocol, the corresponding laboratory analyses, and statistical tests will be carried out.

2.3.1 Metabolic biomarkers analysis

For the analysis of metabolic biomarkers, colorimetric enzymatic methods will be used using the Spinreact® S. A/S A. U (Girona, Spain) laboratory kits, for fasting glucose determination (Cat. No. 1001190), TC (Cat. No. 41022), LDL-C (Cat. No. BSIS51-E), HDL-C (Cat. No. BSIS37-E) and TG (Cat. No. 1001313) (47). The reference points for glucose values and lipid profiles will be taken from the regulations in force in Mexico (64,65).

2.3.2 Gut microbiota analysis

For the analysis of the gut microbiota, the real-time quantitative polymerase chain reaction (qPCR) method will be followed (4,48). First, DNA will be extracted from the collected stool samples, following the protocol for rapid purification of genomic DNA from stool samples. The Qiagen brand commercial kit (1066790ES, USA) will be used. This procedure integrates two stages: lysis and separation of impurities from stool samples, for which Inhibitex Buffer will be used and DNA purification will be carried out by means of centrifugation columns. Once the bacterial DNA samples are obtained, they will be stored and labeled in sterile plastic microtubes (Eppendorf 1.6 mL) at a temperature of -80°C until further analysis.

Next, the purity of the DNA will be verified, and its concentration will be determined using a NanoDrop Lite spectrophotometer (Thermo Scientific, Waltham, MA, USA). 1 µL of the DNA stock of each sample will be placed on the lens of the equipment and the sample will be read at a wavelength of 260 nm for DNA quantification and at 280 nm for protein quantification. The purity will be determined by calculating the index performed by the team, by dividing the reading at 260 nm by the reading at 280 nm and will be considered acceptable in a range of 1.5 to 2. The concentration of the purified coproDNA sample will be measured by their absorbance ratio of 260/280 nm using the same spectrophotometer. This analysis corresponds to the absorbance index of nucleic acids and provides the final concentration in ng/µL (4,48,66).

Once the previous analyzes have been completed, the identification of the gut microbiota will be carried out using the qPCR molecular technique, on the StepOne Applied BioSystems platform, using the SYBR Green reagent as DNA detection chemistry. This reagent is considered an agent that intercalates into the DNA double helix and fluoresces as the DNA copies are synthesized. Therefore, at a higher concentration of the DNA of interest (bacterial), the equipment will record a higher fluorescence signal. In this case, the analysis of interest will be carried out in the V3-V4 hypervariable region of the bacterial 16S rRNA gene. For this analysis, specific primers, which are detailed in Supplementary Material 5 will be used. The bacterial load and relative abundance of the main bacteria present in the intestine (Firmicutes and Bacteroidetes) (4,67,68) will be determined, as well as those related to particular types of diets, for example, *Lactobacillus* and *Bifidobacterium* that are related to healthy, vegetarian and Mediterranean diets (67,69,70), *Faecalibacterium prausnitzii* that is related to healthy diets and an anti-inflammatory effect (41,71–73), as well as *Akkermansia muciniphila*, which besides of being related to anti-inflammatory effects is associated to the consumption of the Mexican pre-Hispanic diet (41,70,72,74,75). The presence of *Prevotella copri* will also be identified, which is one of the bacteria most related to plant-based diets and is considered anti-inflammatory and glucose modulator (75,76). The presence of *Bilophila wadsworthia* will also be identified, as it is related to diets with a high content of foods of animal origin, mainly dairy and meat (71,77), as well as in westernized diets (67,78). Likewise, the presence of *Clostridium coccoides* will be analyzed, as it is related to obesity (48) and a high fat intake (79). Also, *Streptococcus thermophilus* will be included because it is related to dairy consumption (71,80). The exact procedure to follow regarding the qPCR run, as well as the specific conditions and temperatures of the analysis, are presented in the investigation of Rodríguez-Lara et al. (48), which will serve as the guide for this research project.

2.3.3 Evaluation of the adherence to the program

To measure the adherence of the intervened population to the program, an adapted questionnaire will be applied based on that of Gila-Díaz et al. (81), which will consist of the contrast of the recommendations provided with the performance of the behaviors to promote. For example, questions about the type and intensity of physical activity performed and the amount and frequency of consumption of each of the foods included in the behavioral objectives will be included. This questionnaire is shown in Supplementary Material 6.

2.3.4 Statistical analyses

The distribution of the data will be analyzed with the Kolmogorov Smirnov test. Descriptive analysis will be performed, including means, standard deviations, and medians. Next, the effects of the program on the selected variables will be assessed by comparing them between evaluations and between groups with t-student tests for paired and unpaired data, respectively, if a normal distribution is found. For no normally distributed data, the Wilcoxon test (repetitive measures) and the U de Mann Whitney test (independent groups) will be used. For no categorical variables, the chi-squared test will be used. Correlation analyses will also be performed, considering Pearson correlation for normally distributed data and Spearman correlations for no normally distributed data. Likewise, simple, and multiple linear regression models will be carried out, as well as binary logistic regression analysis, to identify relationships and risks between variables. Statistical analysis will be performed at STATA V12® program.

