2.2 Stage 2: Application of the sustainable-psycho-nutritional intervention program

2.2.1 Participants

Once the intervention program has been designed, it will be applied to a sample of Mexican young adults from the south of Jalisco, randomly divided into two groups: an experimental group (n=50) and a control group (n=50). This is based on recommendations for group designs in behavior modification programs (38). The sample size is according to the minimum suggested for nutritional interventions (39,40), and taking into account the possible desertion of the participants during the intervention, which can amount to more than 50% of the initial sample (41). We will include a population between 18 and 35 years old, with Body Mass Index (BMI) values from 18.5 to 40, with or without risk factors for the development of chronic diseases, but without diagnosis with previous pharmacological treatment. The inclusion, exclusion, and elimination criteria are detailed in Supplementary Material 2 in Table SM2.1. Also, for being included in the study cut-off points to identify inadequate consumption and physical activity were established (Table SM2.2). The population will be invited to participate through social networks and posters at strategic points, such as Universities, gyms, and the downtown city. Young adults were selected as the population for this study since they are already considered adults who make autonomous food decisions, but at the same time, their young age makes them susceptible to behavioral modification. In addition, they represent parents or future parents, as well as the active population of Mexico, so providing nutritional-sustainable education to these people could generate long-term benefits for their health and that of their families (21,42,43).

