2.2.2 Procedure

Participants will be evaluated following the nutritional care process model (44). The first evaluation will be performed at the beginning of the intervention at baseline, and according to individual requirements, the behavioral objectives will be individually adapted and will be addressed for 7 weeks, considering 2 objectives per week, thus providing 2 weekly educational workshops. Also, personalized food plans will be prescribed, according to the linear programming optimization (29,30) performed at MATLAB®.

After 7 weeks of educational and nutritional intervention, at week 8, the experimental population will be divided into two sub-groups, where one group will stop being intervened completely (n = 25), and another will continue to receive messages through the mobile application (n = 25) for 8 weeks. Finally, at week 15, a final evaluation will be carried out. The study design is shown in Figure 2. Participants will be evaluated in the regard of Anthropometric, Biochemical, Clinical, Dietetics, Environmental, Socioeconomic level and cultural aspects,

Nutritional-sustainable knowledge, Behavioral aspects, and Physical activity (ABCD-ESNBP). These aspects will be evaluated according to the nutritional care process model, thus identifying the problem of the population, establishing the etiology, and stating the signs and symptoms (44).

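### Section 2.3.4 counts paired within-group and unpaired between-group tests equally as tests of the programme effect, names neither as deciding, and specifies no between-group test that uses the baseline value

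*Combined protocol and SAP*

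**What the plan says.** Section 2.3.4 is the whole analysis plan. Its operative sentence is that "the effects of the program on the selected variables will be assessed by comparing them between evaluations and between groups with t-student tests", with the paired test for the comparison between evaluations and the unpaired test for the comparison between groups. The Wilcoxon and Mann-Whitney tests repeat this pair for non-normal data. Nothing here or elsewhere ranks the two comparisons. The section does not say whether the unpaired test is applied to follow-up values or to change, and it mentions no baseline covariate or group-by-time term. Linear and logistic regression are listed only for another purpose: "as well as binary logistic regression analysis, to identify relationships and risks between variables".

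Section 2.2.1 provides a control group, with participants "randomly divided into two groups: an experimental group (n=50) and a control group (n=50" (the sentence goes on from there). The same section says that "for being included in the study cut-off points to identify inadequate consumption and physical activity were established"; the details are in Tables SM2.1 and SM2.2. It also expects dropout "which can amount to more than 50% of the initial sample". On the baseline value, section 2.2.2 says: "The first evaluation will be performed at the beginning of the intervention at baseline". No screening measurement separate from that evaluation is described.

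**The concern.** A before-after change within the experimental group contains the programme effect plus everything else that changes with time: season, repeated measurement, and awareness of being studied. Only the comparison with the control group removes these. Because the plan makes the paired test an assessment of programme effect in its own right, a report could follow the plan and still present a time effect as a benefit. The hypotheses in the Introduction make this likely, since they are worded as movements (falls in glucose and lipids, lower footprints), which a paired p-value appears to confirm directly.

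Variables used for entry carry a second risk. People are admitted because their activity is low or their intake inadequate. If the value that admitted them is also the analysed baseline, part of the later improvement is regression to the mean.

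The plan also leaves open which between-group test is run. Power depends on that choice, and the trial may lose half its sample.

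**Working it through.** **No figure to reproduce.** The documents give no alpha, power, effect size, SD or baseline-to-follow-up correlation. Only the 50 per group, the possible loss of half (hence 25) and the entry criteria come from the plan. All other inputs are assumed: unit SD, normal data, correlation r, two-sided 5% tests with only improving results counted (nominal 2.5%), and no programme effect in steps 1 and 2.

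**1. Outcome not used for entry, common drift δ in both arms.** The paired test has noncentrality δ√n / √(2(1−r)) on n−1 degrees of freedom. For n=50, δ=0.1, r=0.4 this is 0.1×7.07/1.095 = 0.65, giving 9%. For δ=0.2, r=0.7 it is 0.2×7.07/0.775 = 1.83, giving 43%. At n=25 the same two settings give 6% and 24%. The arms are independent, so the pattern of experimental arm significant and control arm not has probability p(1−p). At n=50: 0.092×0.908 = 8% to 0.4325×0.5675 = 25%. At n=25: 6% to 18%.

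**2. Entry variable, screening value used as baseline.** Admit those below a cut-off c. Their mean baseline is −φ(c)/Φ(c), and the expected improvement is (1−r)φ(c)/Φ(c). If half of people qualify (c=0) this is 0.6×0.798 = 0.48 SD at r=0.4 and 0.3×0.798 = 0.24 SD at r=0.7. If 93% qualify (c=1.5) it is 0.08 and 0.04 SD. Simulated significance of the experimental-arm paired test for r=0.4 to 0.7:

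| Share qualifying | n=50 | n=25 |
|---|---|---|
| 93% | 6–8% | 4–6% |
| 84% | 12–21% | 8–12% |
| 50% | 61–92% | 35–65% |

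Applying p(1−p), experimental significant and control not occurs in 5–24% of trials at n=50 and 4–25% at n=25. At the extreme (92%, n=50) it is only 0.92×0.08 = 7%, because the control arm improves as well.

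Two conditions govern this table. If baseline is measured afresh after screening, the rate returns to 2.3–2.7%. The food-intake criterion also does not say how many groups must be inadequate. With 13 independent food groups, half of people inadequate on each and r=0.4, the rate for any one group is 2.5% if a single inadequate group suffices and 92% if all 13 must be. Physical activity is a criterion of its own.

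**3. Power of the between-group choices.** With 25 per arm and d=0.6, noncentrality is (0.6/s)√(25/2), where s is the SD of the analysed quantity.

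| Analysis | s | r=0.3 | r=0.5 | r=0.6 |
|---|---|---|---|---|
| Follow-up value | 1 | 55% | 55% | 55% |
| Change | √(2(1−r)) | 42% | 55% | 64% |
| ANCOVA | √(1−r²) | 59% | 67% | 74% |

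Change scores lose power against follow-up values when r is below 0.5. ANCOVA is the most powerful of the three at each r shown.

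**The case against.** The plan has a control group and a between-group test, and it joins the two comparisons with *and*, so a sensible analyst would rely on the contrast with control. The multiple regression could in principle be an ANCOVA. What stands is that a valid between-group test is present. But nothing makes it the deciding one, and the regression names no outcome, group term or baseline covariate.

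Several stronger readings are tempting and should be resisted.

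- A reader might take 92% as the trial's false-positive rate. It is the extreme of one assumed scenario, for one arm, on an entry variable, without dropout.
- A reader might carry the entry-variable figures over to glucose, lipids or microbiota. None of these has a cut-off in Table SM2.2, so only the drift figures apply. Footprints derive from diet, so some carry-over is possible, but it was not computed.
- A reader might infer that any outcome-related loss invalidates the between-group test. In simulation with half completing, the same dependence in both arms left the error at 4.5–5.0%. Dependence in the experimental arm only (odds ratio 1.65 or 2.7 per SD) raised it to 13–14% or 32–33%.
- A reader might treat any group-by-time model as baseline adjustment. With two time points and complete data, an unconstrained group-by-time term is the change-score contrast, which has less power than the follow-up test at r=0.3.

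**Conclusion.** The point holds as a gap in specification that should be closed before data are seen. As written, section 2.3.4 allows a within-group change to be reported as a programme effect and leaves the between-group test undefined with respect to baseline. With no programme effect, the experimental-arm paired test is significant in 9–43% of trials at 50 per arm and 6–24% at 25, for an outcome not used for entry under 0.1–0.2 SD of common drift. For an entry variable whose screening value is the baseline, the ranges are about 6–92% and 4–65%. These rest on assumed drift, correlation and qualifying share; they show scale and do not predict this trial's error.

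The documents do not support the reading that the trial lacks a valid test. The between-group comparison holds about 5% if allocation is random and loss does not depend on outcome differently in the two arms. The first condition deserves care, because section 2 says "It is proposed to carry out a quasi-experimental longitudinal study of three stages" while section 2.2.1 describes random division.

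**What to change.** Add to section 2.3.4 wording such as:

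> The efficacy test for each continuous outcome is the difference between the randomised groups at follow-up, adjusted for that outcome's baseline value by ANCOVA (or an equivalent longitudinal model with the baseline mean constrained equal across groups). Skewed outcomes are log- or rank-transformed before the same model. Paired within-group changes are descriptive, and no conclusion about programme effect is drawn from them.

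The cost is analysis wording only, since baseline is already measured. There are three downsides. Within-group p-values can no longer be cited as evidence of effect. The power gain is small where the baseline correlation is low (55% to 59% at r=0.3). And adjustment does not repair the elimination of non-completers in Table SM2.1 if completion depends on outcome differently by arm: in the experimental-arm-only simulation above, ANCOVA still gave 10–13% or 23–29% false positives.

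The design label, the rule for how many Table SM2.2 variables must be inadequate, and the pooling of the two experimental subgroups at week 15 are separate questions that this change does not settle.
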